## 6.5 Dietary Restrictions

There are no dietary restrictions on this study. Subject should maintain a normal diet unless modifications are required to manage an AE such as diarrhea, nausea or vomiting.

## 6.6 Pregnancy and Contraception

### 6.6.1 Contraception

Pembrolizumab and/or axitinib may have adverse effects on a fetus in utero. Furthermore, it is not known if pembrolizumab and/or axitinib have transient adverse effects on the composition of sperm.

For this trial, male subjects will be considered to be of non-reproductive potential if they have azoospermia (whether due to having had a vasectomy or due to an underlying medical condition).

Female subjects will be considered of non-reproductive potential if they are either:

- (1) Postmenopausal (defined as at least 12 months with no menses without an alternative medical cause; in women <45 years of age, a high follicle stimulating hormone (FSH) level in the postmenopausal range may be used to confirm a post-menopausal state in women not using hormonal contraception or hormonal replacement therapy. In the absence of 12 months of amenorrhea, a single FSH measurement is insufficient.);

OR

- (2) Have had a hysterectomy and/or bilateral oophorectomy, bilateral salpingectomy or bilateral tubal ligation/occlusion, at least 6 weeks prior to screening;

OR

- (3) Has a congenital or acquired condition that prevents childbearing.

Female and male subjects of reproductive potential must agree to avoid becoming pregnant or impregnating a partner, respectively, while receiving study drug and for 120 days after the last dose of study drug by complying with one of the following:

(1) Practice abstinence† from heterosexual activity;

OR

(2) Use (or have their partner use) acceptable contraception during heterosexual activity.

**Acceptable methods of contraception are‡:**

Single method (1 of the following is acceptable):

- intrauterine device (IUD)
- vasectomy of a female subject's male partner
- contraceptive rod implanted into the skin

Combination method (requires use of 2 of the following):

- diaphragm with spermicide (cannot be used in conjunction with cervical cap/spermicide)
- cervical cap with spermicide (nulliparous women only)
- contraceptive sponge (nulliparous women only)
- male condom or female condom (cannot be used together)
- hormonal contraceptive: oral contraceptive pill (estrogen/progestin pill or progestin-only pill), contraceptive skin patch, vaginal contraceptive ring, or subcutaneous contraceptive injection

†Abstinence (relative to heterosexual activity) can be used as the sole method of contraception if it is consistently employed as the subject's preferred and usual lifestyle and if considered acceptable by local regulatory agencies and IRBs/ERCs. Periodic abstinence (e.g., calendar, ovulation, sympto-thermal, post-ovulation methods, etc.) and withdrawal are not acceptable methods of contraception.

‡If a contraceptive method listed above is restricted by local regulations/guidelines, then it does not qualify as an acceptable method of contraception for subjects participating at sites in this country/region.

Subjects should be informed that taking the study medications may involve unknown risks to the fetus (unborn baby) if pregnancy were to occur during the study. In order to participate in the study, subjects of childbearing potential must adhere to the contraception requirement (described above) from the day of study medication initiation (or 14 days prior to the initiation of study medication for oral contraception) throughout the study period up to 120 days after the last dose

of trial therapy. If there is any question that a subject of childbearing potential will not reliably comply with the requirements for contraception, that subject should not be entered into the study.

#### **6.6.2 Use in Pregnancy**

If a subject inadvertently becomes pregnant while on study treatment, the subject will be immediately discontinued from study treatment. The site will contact the subject at least monthly and document the subject's status until the pregnancy has been completed or terminated. The outcome of the pregnancy will be reported to Merck without delay and within 24 hours if the outcome is a SAE (e.g., death, abortion, congenital anomaly, or other disabling or life-threatening complication to the mother or newborn). The study Investigator will make every effort to obtain permission to follow the outcome of the pregnancy and report the condition of the fetus or newborn to Merck. If a male subject impregnates his female partner, the study personnel at the site must be informed immediately and the pregnancy must be reported to Merck and followed as described in Section 7.8.

#### **6.6.3 Use in Nursing Women**

It is unknown whether pembrolizumab is excreted in human milk. Since many drugs are excreted in human milk, and because of the potential for serious adverse reactions in the nursing infant, subjects who are breast-feeding are not eligible for enrollment.

#### **6.6.4 Pregnancy tests**

All women who are being considered for participation in the trial, and who are not surgically sterilized or postmenopausal, must be tested for pregnancy within 72 hours of each cycle of trial treatment and 30 days post treatment. If a urine test is positive or not evaluable, a serum test will be required. Subjects must be excluded/discontinued from the study in the event of a positive or borderline-positive test result.

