#### 6.1.1 Pretreatment Period

##### 6.1.1.1 Screening

The Screening procedures and assessments must be completed within 28 days of the first dose of pembrolizumab-based therapy.

Screening procedures and assessments:

- Demographics
- Complete medical history
- Baseline conditions assessment
- Complete physical examination
- Baseline medications taken within 14 days of Day 1. For stool correlative analysis, it should be noted if antibiotics were taken within 90 days before the first dose of study drug(s).
- Vital signs, height, and weight
- ECOG performance status within 7 days of Cycle 1 Day 1
- Laboratory assessments (within 10 days of treatment initiation):
  - Complete blood count (CBC) with differential and platelet count

- Blood chemistry assessment, including:
  - Alkaline phosphatase (ALP), aspartate aminotransferase/alanine aminotransferase (ALT/AST), total bilirubin, calcium, phosphorus, blood urea nitrogen (BUN), creatinine, total protein, albumin, fasting glucose, potassium, sodium, chloride, bicarbonate, uric acid, lactate dehydrogenase (LDH)
- Thyroid function tests: thyroid-stimulating hormone (TSH), free thyroxine (FT4), triiodothyronine (T3)
- Coagulation assessment (prothrombin time [PT], partial thromboplastin time [PTT], and international normalized ratio [INR])
- Urinalysis (including microscopic exam if abnormal results are noted)
- Serum or urine pregnancy test within 72 hours prior to the start of study drug
- Imaging evaluation (computed tomography [CT] chest, abdomen and pelvis; magnetic resonance imaging [MRI] if CT is contraindicated; IV contrast given unless contraindicated; Bone scan if clinical indicated; MRI brain if clinically indicated), for tumor assessment
- Request of archival specimen originally obtained prior to consent for banking (formalin-fixed paraffin-embedded [FFPE] tumor specimen, if available)
- Biopsy of primary or metastatic lesion (see Section 3.3.1, Inclusion Criteria)
- Blood for correlative studies (including immune monitoring)
- Correlative Studies Stool Collection

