#### 6.1.2.6 Postoperative Therapy, Day 1 of Each Cycle

Following CN/MET, continuation of pembrolizumab-based therapy for patients who achieved pre-operative CR/PR/SD will proceed as follows:

- Subjects with an R0 resection (NED, margins negative) or R1 resection (microscopic disease, margins positive) will continue receiving their assigned pembrolizumab-based combination therapy for up to 9 cycles or until disease progression, death, unacceptable toxicity, or withdrawal of consent, whichever occurs first
- Subjects with an R2 resection (macroscopic disease after surgery), or who had a pre-operative CR but did not undergo CN, will continue receiving their assigned pembrolizumab-based combination therapy for up to 18 cycles or until disease progression, death, unacceptable toxicity, or withdrawal of consent, whichever occurs first.
- Subjects may resume therapy following CN/MET as soon as 21 days following surgery (subjects with metastatic disease who have a CR during the preoperative period and therefore do not undergo MET will have no interruption in their therapy). Prior to resuming therapy, the subject must be evaluated by their surgeon and appropriate wound healing must be documented. Subjects with wound healing complications that have not resolved with 42 days of CN and/or MET will discontinue study participation. Any subject who

cannot resume study therapy within 42 days of CN/MET will discontinue study participation.

Perform the following study procedures on Day 1 of each cycle ( $\pm 3$  days) unless stated otherwise:

- Directed physical examination
- Vital signs and weight
- ECOG performance status
- Evaluation of AEs
- Concomitant medications
- CBC with differential and platelet count
- Blood chemistry assessment, including:
  - ALP, ALT/AST, total bilirubin, calcium, phosphorus, BUN, creatinine, total protein, albumin, fasting glucose, potassium, sodium, chloride, bicarbonate, uric acid, LDH
- Thyroid Function Tests: TSH, FT4, T3
- Blood for correlative studies (including immune monitoring) at week 15 only
- Urinalysis (including microscopic exam, if abnormal results are noted)
- Treatment:
  - All cohorts, metastatic disease and achieved CR:
    - Pembrolizumab 400 mg IV (Day 1) Q6W
  - Cohort A (all other subjects continuing therapy):
    - Pembrolizumab 400 mg IV (Day 1) Q6W
  - Cohort B (all other subjects continuing therapy):
    - Pembrolizumab 400 mg IV (Day 1) Q6W
    - Axitinib (Days 1 - 42). Dose titration per standard of care

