#### 6.1.3.2 Safety Follow-Up

The mandatory Safety Follow-up Visit should be conducted 30 days (+7 days) after the last dose of study treatment or before initiation of a new anticancer treatment, whichever comes first. All AEs that occur prior to the Safety Follow-up Visit should be recorded. Subjects with an AE of Grade >1 will be followed until the resolution of the AE to Grade 0-1 or until the beginning of a new anticancer therapy, whichever occurs first. Serious AEs (SAEs) that occur within 90 days of the end of treatment or before initiation of a new anticancer treatment should also be followed and recorded.

The following procedures will be performed at the Safety Follow-up Visit:

- Directed physical examination
- Vital signs and weight
- ECOG performance Status
- Evaluation of AEs
- Concomitant medications
- Urinalysis (including microscopic exam if abnormal results are noted)
- CBC with differential and platelet count
- Blood chemistry assessment, including:
  - ALP, ALT/AST, total bilirubin, calcium, phosphorus, BUN, creatinine, total protein, albumin, fasting glucose, potassium, sodium, chloride, bicarbonate, uric acid, LDH
- Thyroid function tests: TSH, FT4, T3

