#### **6.1.3.3 1-Year Follow-Up**

Those subjects who complete preoperative therapy and achieve either CR/PR/SD with R0 or R1 resection, and complete 1 year (9 cycles) of continued pembrolizumab-based therapy will be followed for up to 1 additional year (12 months), or until disease progression, death, unacceptable toxicity or withdrawal of consent, whichever occurs first.

Those subjects who complete preoperative therapy and achieve either CR/PR/SD with R2 resection, or achieve a pre-operative CR but do not undergo CN, and complete 2 years (18 cycles) of continued pembrolizumab-based therapy (400 mg Q6W) will be followed for up to 12 additional months, or until disease progression, death, unacceptable toxicity or withdrawal of consent, whichever occurs first.

During the 1-year follow-up period, the following procedures will be performed every 12 weeks(±14 days) from the date of last dose of study treatment or discontinuation:

- Directed physical examination
- Vital signs and weight
- ECOG performance status
- Evaluation of AEs
- Concomitant medications

- CBC with differential and platelet count
- Blood chemistry assessment, including:
  - ALP, ALT/AST, total bilirubin, calcium, phosphorus, BUN, creatinine, total protein, albumin, fasting glucose, potassium, sodium, chloride, bicarbonate, uric acid, LDH
- Thyroid Function Tests: TSH, FT4, T3
- Urinalysis (including microscopic exam, if abnormal results are noted)
- Imaging evaluation (CT chest, abdomen and pelvis; MRI if CT is contraindicated; IV contrast given unless contraindicated; Bone scan if clinical indicated; MRI brain if clinically indicated) for tumor assessment will be performed as specified in study flow chart [Table 7])

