- Includes alkaline phosphatase (ALP), aspartate aminotransferase/alanine aminotransferase (ALT/AST), total bilirubin, calcium, phosphorus, blood urea nitrogen (BUN), creatinine, total protein, albumin, fasting glucose, potassium, sodium, chloride, bicarbonate, uric acid, lactate dehydrogenase (LDH)
- Laboratory evaluations may be omitted if they were already performed within 7 days of Cycle 1, Day 1
- Window for these specific assessments is within the 14 days prior to CN and/or MET
- Women of childbearing potential require a negative urine test within 72 hours prior to the first dose of study treatment. Serum test is only required if urine test is positive or is not evaluable. Additional urine pregnancy testing can be conducted if required by local regulations or clinically indicated.

- f. Administered for up to 1 year (9 cycles) (for patients who undergo CN/MET with R0 or R1 resection), or up to 2 years (18 cycles) (for patients who undergo CN/MET with R2 resection or who had a pre-operative CR but did not undergo CN), or until death, disease progression, unacceptable toxicity, or withdrawal of consent.
- g. To be done every 2 cycles (i.e., about every 3 months) during postoperative pembrolizumab-based treatment
- h. If prior scan was done within 6 weeks, does not have to be repeated (per physician discretion)
- i. Those subjects who undergo CN/MET with R0 or R1 resection who complete 1 year (9 cycles) of postoperative pembrolizumab-based therapy, or those patients who undergo CN/MET with R2 resection or who had a pre-operative CR but did not undergo CN and complete 2 years (18 cycles) of postoperative pembrolizumab-based therapy, will have scans Q12W for up to 12 additional months, or until disease progression, death, unacceptable toxicity or withdrawal of consent, whichever occurs first.
- j. Imaging evaluation (CT chest, abdomen and pelvis; MRI if CT is contraindicated; IV contrast given unless contraindicated; Bone scan if clinically indicated; MRI brain if clinically indicated), for tumor assessment
- k. In subjects who complete postoperative pembrolizumab-based therapy: end of treatment visit will be performed within 7 days of the last dose of study drug or discontinuation
- l. In subjects who complete postoperative pembrolizumab-based therapy: additional safety follow-up visit is not necessary; the follow-up visit will be done during the 12 month follow-up period
- m. At the time of disease progression (subjects will require additional consent)

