### **6.8 Laboratory Procedures/Assessments**

Details regarding specific laboratory procedures/assessments to be performed in this trial are provided below. The total amount of blood/tissue to be drawn/collected over the course of the

trial (from pre-trial to post-trial visits), including approximate blood/tissue volumes drawn/collected by visit and by sample type per subject can be found in the laboratory manual.

Refer to the Trial Flow Chart - Section 6.2 for the schedule of laboratory assessments.

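### Section 6.6.4 mandates a pregnancy test at every cycle and 30 days after treatment, but Table 7 and the Section 6.1 visit lists schedule only one, before the first dose

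*Combined protocol and SAP*

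**What the plan says.** Section 6.6.4 sets the duty. It covers women who are neither postmenopausal nor surgically sterilized, and says that they "must be tested for pregnancy within 72 hours of each cycle of trial treatment and 30 days post treatment". A serum test follows if the urine test is positive or cannot be evaluated, and a positive or borderline result means exclusion or discontinuation.

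The schedule says something else. The screening list in 6.1.1.1 has one entry: "Serum or urine pregnancy test within 72 hours prior to the start of study drug". The pregnancy-test row of Table 7 has a single mark, under Screening. Its footnote requires one negative urine test before the first dose and then adds: "Additional urine pregnancy testing can be conducted if required by local regulations or clinically indicated".

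Section 6.8 tells staff which document sets the timing: "Refer to the Trial Flow Chart - Section 6.2 for the schedule of laboratory assessments". Table 8 in that section lists urine and serum pregnancy tests but gives no repeat times.

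**The concern.** The same test is mandatory at every cycle in one section and conditional after the first dose in another. The conditional version sits in the flow chart, which is what a coordinator uses to plan visits. Someone who follows Table 7 and the 6.1 lists to the letter would not meet 6.6.4.

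What is at stake is participant safety, not inference. Section 6.6.1 states that pembrolizumab and/or axitinib may harm a fetus. Treatment after surgery can run for 9 or 18 cycles of six weeks. The contraception rules and exclusion criterion 20 lower the chance of pregnancy. Sections 6.3.1, 6.6.2 and 7.8 deal with a pregnancy once it is known, and the stopping criterion in 6.3.1 is itself a confirmed positive serum test. Apart from 6.6.4, the plan has no routine test that would find an unrecognized pregnancy during treatment.

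**Working it through.** The plan gives no figure to reproduce. The check is a side-by-side reading and then a count.

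**Step 1. Where a pregnancy test appears in the schedule**

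- Screening (6.1.1.1, and the Screening column of Table 7): one test, within 72 hours before the first dose. Inclusion criterion 10 matches.
- Preoperative Cycles 1, 2 and 3 (6.1.2.1 to 6.1.2.3): none. The screening test can serve Cycle 1.
- Week 10 visit and surgery (6.1.2.4, 6.1.2.5): none.
- Postoperative cycles (6.1.2.6): the list opens with "Perform the following study procedures on Day 1 of each cycle" and includes blood count, chemistry, thyroid tests and urinalysis, but no pregnancy test.
- End of treatment, safety follow-up and 1-year follow-up (6.1.3.1 to 6.1.3.3): none.

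The empty cells in Table 7 could in principle come from damage to the extracted table. That is not the explanation here, because the footnote wording and each of the 6.1 lists independently give the same single test.

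**Step 2. Inputs for the count**

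- Preoperative cycles: 3 (Section 5.1).
- Postoperative cycles: up to 9 after R0 or R1 resection; up to 18 after R2 resection, or after a preoperative complete response without nephrectomy (Sections 3.1 and 5.1).
- Tests under 6.6.4: one per cycle, plus one at 30 days post treatment.
- Tests scheduled in Table 7 and 6.1: one, counted as the Cycle 1 test.

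**Step 3. Count for one woman covered by 6.6.4**

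Required = preoperative cycles + postoperative cycles + 1. Unscheduled = required − 1.

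- 9 postoperative cycles: 3 + 9 + 1 = 13 required; 13 − 1 = 12 unscheduled.
- 18 postoperative cycles: 3 + 18 + 1 = 22 required; 22 − 1 = 21 unscheduled.
- Preoperative cycles only: 3 + 1 = 4 required; 4 − 1 = 3 unscheduled.

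The first two are ceilings, because progression, toxicity or withdrawal ends treatment sooner.

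**Step 4. Who has a 30-day visit at which the last test could be done**

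Section 6.1.3.2 says: "The mandatory Safety Follow-up Visit should be conducted 30 days (+7 days) after the last dose of study treatment". Its procedure list has no pregnancy test. For subjects who complete postoperative therapy, a Table 7 footnote says: "additional safety follow-up visit is not necessary; the follow-up visit will be done during the 12 month follow-up period". The follow-up rows of the Abstract and Section 3.5 fit that footnote. They attach the 30-day visit to subjects with progression (Section 3.5 adds a visit within 30 days for certain other removals) and send completers to 12 months of follow-up. Adding a line to 6.1.3.2 would therefore cover women who stop early but would probably miss those who complete.

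**The case against.** The best reply is that the two texts can be obeyed together. Section 6.6.4 remains in force, nothing in Table 7 forbids a further test, and the footnote allows one when clinically indicated. Adverse-event review and a directed examination take place on Day 1 of each cycle and could prompt it. This is a single-centre study, and the number of women concerned is not stated. Table 7, the 6.1 lists and inclusion criterion 10 also agree with one another, so 6.6.4 may be the text that is out of line.

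Much of this stands, and it limits the point. The tests are unscheduled, and a reader who infers that the protocol rules them out, or that no woman would be tested on treatment, goes further than the text allows. But a test prompted by symptoms does not replace a routine one, and staff are directed to the schedule that leaves the routine one out. The documents do not say which version was intended, so the mismatch has to be settled.

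A reader might make two further inferences, and neither is supported:

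- That 6.1.3.2 and the Table 7 footnote are equally likely readings for completers. The Abstract and Section 3.5 side with the footnote, so the better reading is that completers have no separate 30-day visit.
- That one can state how many days late the final test would be for completers. Follow-up visits are counted "from the date of last dose of study treatment or discontinuation", but 6.6.4 does not say whether its 30 days run from the last dose or from the end of the last 42-day cycle. Any such figure would rest on an anchor that the plan does not give.

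**Conclusion.** The inconsistency is real and lies in current text. Section 6.6.4 requires repeat pregnancy testing, while the flow chart, its footnote and the visit lists schedule a single pre-dose test. If staff work from the flow chart alone, up to 12 of 13 or 21 of 22 mandated tests are left out for a woman who receives every planned cycle, and 3 of 4 for a woman who receives only the preoperative cycles. These counts assume one test per cycle and that the screening test serves as the Cycle 1 test. The number of women affected cannot be worked out from the documents.

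No endpoint, analysis population, sample size or decision rule is touched. It should still be corrected, because the omission concerns a safety test that the protocol itself makes mandatory and the correction is cheap.

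**What to change.** Align the schedule with 6.6.4, which is the safer direction. For women of childbearing potential:

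- Add a urine pregnancy test (serum if positive or not evaluable) within 72 hours of Day 1 of every cycle to Table 7 and to 6.1.2.2, 6.1.2.3 and 6.1.2.6. The existing pre-dose test covers Cycle 1.
- Add the 30-day post-treatment test to Table 7 and 6.1.3.2.
- Change the Table 7 footnote so that testing at these times is required instead of permitted.
- State how women who complete postoperative therapy get the 30-day test, for example by a local urine test, and say in 6.6.4 from which date the 30 days run.

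If the sponsor intended only a pre-dose test, 6.6.4 is the section to amend, with the reason given.

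The drafting cost is small: additional marks in an existing table row, one footnote, one line in each of four visit lists and a sentence or two on the final test. The burden on participants is one urine test per cycle in a subgroup, already required by 6.6.4. For completers, the 30-day test may mean one extra contact.
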